10 MEASUREMENT OF EFFECT

10.1 Criteria for Tumor Response

Tumor response will be evaluated and recorded according to RECIST v1.1 (27)

10.2 Imaging

Only imaging of the initial sites of disease is required at subsequent time points to provide tumor measurements for assessment of antitumor effect. Brain imaging after initiation of study therapy is only required for patients who have a history of brain metastasis.

The same type of imaging used at baseline should be used at each scheduled assessment which will be performed at the end of every other 4-week cycle (ie, approximately every 8 weeks). At the investigator's discretion, additional imaging may be performed when clinically indicated.

10.3 Criteria for Tumor Response

In the event of a PR or CR, the imaging used when the response was first documented must be repeated at the time of the next scheduled imaging, ie, in about 8 weeks, to confirm tumor response. (At the investigator's discretion, confirmatory scans can be performed sooner, but no less than 4 weeks following the imaging indicating the PR or CR.)

10.4 Central Review for Imaging Interpretation

Centralized radiologic review for response evaluation will be conducted.

11 CORRELATIVE STUDIES

11.1 Participation in Correlative Studies

Tumor samples archived following the most recent biopsy or surgery will be used for the correlative studies. Participation in the correlative studies using archived tumor samples, **if available**, is mandatory.

11.2 Collection, Immunostaining, and Distribution of Samples

• The study team will coordinate collection of all correlative tumor samples. Additionally, the study team will ensure that samples are de-identified prior to distribution to the laboratories performing the correlative studies.

- Massey Cancer Center Clinical and Translational Research Lab (CTRL) will receive, process, store, and/or distribute tumor samples to the laboratories performing the correlative studies as needed based on the plans outlined in Section 11.3.
- Questions regarding study requirements should be directed to the study team. The principal investigator should be contacted in the event that a correlative sample must be missed or is found to be inadequate for submission.
- Collection and distribution of all tumor samples will be logged by the study team in OnCore.

11.3 Archived Tumor Samples

Expression of multiple cellular proteins will be analyzed by IHC methods using samples from tumor archived at the time of the most recent diagnostic biopsy or surgery.

11.3.1 Tumor Sample Requirement

When sufficient archived tumor tissue is available:

- Request a tumor block from archived samples from **the most recent diagnostic biopsy or surgical resection**.
- If an outside hospital does not transfer blocks of tissue, request 10 unstained slides, each with specimen 4 microns thick.
- To obtain an archived biopsy specimen from an outside hospital:
 - Request that a tissue block be sent to the study team; the study team will coordinate with VCU Anatomic Pathology for slide preparation.
 - If the outside hospital does not transfer blocks of tissue, request delivery of 10 unstained slides, each with specimen 4 microns thick.
- The study team should request tumor samples **by the end of cycle 2** (ie, within about 8 weeks after initiation of study treatment).

11.3.2 Tumor Sample Labeling

The tumor sample should be labeled with the following information:

- Study number
- Patient study identification number
- Date of tumor sample collection

11.3.3 Immunostaining of Unstained Slides

All unstained slides will be delivered to the CTRL where immunostains for total CD95 expression and the expression of other proteins of interest will be performed.

11.3.4 Interpretation of Immunostain Results

After staining, slides stained with validated antibodies for standard IHC will be returned to the VCU Anatomic Pathology for interpretation by a clinical pathologist. Results will be communicated to the CTRL and the study team.

12 STUDY CALENDARS

The schedule of tests, exams, disease assessments, collection of samples for correlative studies, and study treatment are listed on 2 tables: requirements during screening through treatment cycle 1 on Table 19 and requirements during remaining treatment beginning with cycle 2 and continuing through study follow-up on Table 20.

Table 19. Study	y Calendar - Scree	ening Through Tre	atment Cycle 1

Tests, Exams, and Other Requirements	Screening (Days Prior to Cycle 1, Day 1)			Study Treatment – Cycle 1				
	Within 28 Days	Within 14 Days	Within 7 Days	Day 1 ^A	Day 8 ^B	Day 15 ^B	Day 22 ^B	Day 29 ^B (If cycle wa extended) ⁶
Informed Consent	Х							,
Demographics	Х							
Medical/Surgical History	Х							
Height	Х							
Weight		Х		Х	Х	Х	Х	Х
Vital Signs		Х		Х	Х	Х	Х	Х
BP		Х		Х	Х	Х	Х	Х
Performance Status		Х		Х	Х	Х	Х	Х
Baseline Conditions/Symptoms		Х						
AE Assessment					Х	Х	Х	Х
Concurrent Medications ^D		Х			Х	Х	Х	Х
Physical Exam		Х		Х	Х	Х	Х	Х
CBC with Differential		Х		Х	Х	Х	Х	Х
Platelet Count		Х		Х	Х	Х	Х	Х
Serum Chemistry ^E		Х		Х	XF	XF	XF	XF
aPTT and INR		Х						
Lipase		Х						
TSH and T4		Х						
Serum Pregnancy Test ^G			Х					
Urinalysis for protein		XH						
12-Lead ECG	Х				Х	Х	Х	Х
LVEF Assessment ^J	Хĸ							
Imaging/Disease Assessment	XL							
Correlative Tumor Sample Collection					-	Х ^м		
AR-42 PO ^N				Once daily 3 days/week during 1 st 3 weeks			Xo	
Pazopanib PO ^N						Xo		
Study Med Diary Review/Pill Count				Х	Х	Х	Х	Х

Table 19 Footnotes:

- A. Except for BP and vital signs, baseline evaluations performed within 1 week prior to initiation of study treatment do not need to be repeated on cycle 1, day 1.
- B. Within +/- 24 hours.
- C. Day 29 requirements only apply to patients who had a treatment interruption earlier in the cycle that required extending the cycle beyond 28 days (up to a maximum of 35 days).
- D. Include over-the-counter medications.
- E. Serum chemistry includes the following panels and tests: basic metabolic panel (sodium, potassium, carbonate, chloride, glucose, calcium, BUN, and creatinine); hepatic panel (ALT, AST, ALP, total bilirubin, direct bilirubin, albumin, and total protein); and magnesium and phosphorous.
- F. Refer to Table 8 for instructions regarding increased frequency of liver function monitoring (weekly for at least 4 weeks) when pazopanib-related elevations (AST, ALT, bilirubin) occur.
- G. Only required for WCBP; see Section 4.1.12 for the definition of WCBP.
- H. If urinalysis reading for protein is ≥ 2+ (100 mg/dL), a 24-hour urine sample must be collected and tested (see Section 4.1.6 for related eligibility criterion).
- I. Refer to Section 4.2.13, Section 6.8, and Table 7 for instructions related to QTc interval prolongation.
- J. Assessment may be performed by echocardiogram or by a nuclear study (eg, MUGA scan; first-pass technique).
- K. Determination of LVEF is required within 3 months prior to cycle 1, day 1 study treatment.
- L. Baseline imaging **must be contrast-enhanced** and include the following:
 - Chest CT, CT or MRI of abdomen and pelvis, and all other suspected sites of disease **within 28 days** prior to initiation of study treatment; for patients with a CT contrast allergy, the chest CT may be performed without contrast or, if the chest is not a known site of disease, a chest x-ray may be used
 - Brain CT or MRI within 8 weeks prior to initiation of study treatment
- M. Collection of tumor samples archived following the most recent biopsy or surgery; tumor samples must be requested by the end of cycle 2 (Section 11).
- N. Refer to Sections 6.1 through 6.6 for treatment-related instructions including the AR-42 and pazopanib dose levels.
- O. If cycle has been extended to 5 weeks, AR-42 doses must be given during the 1st 4 weeks of the cycle allowing a 1-week AR-42 rest period (Section 6.2.1); pazopanib continues daily.

Tests, Exams, and Other Requirements	Cycle 2		Cycle 3	Cycle 4	End of	End of
	Day 1 ^A	Day 15 ^B	Day 1 ^A	Day 1 ^A	Treatment ^c	30-Day Follow-Up
Weight	Х		Х	Х	Х	
Vital Signs	Х		Х	Х	Х	
BP	Х	Х	Х	Х	Х	
Performance Status	Х		Х	Х	Х	
Assessment of AEs	Х		Х	Х	Х	XD
Concurrent Medications ^E	Х		Х	Х	Х	
Physical Exam	Х		Х	Х	Х	
CBC with Differential	Х	Х	Х	Х	Х	
Platelet Count	Х	Х	Х	Х	Х	
Serum Chemistry ^F	XF	XF	XF	X ^F	Х	
Lipase	Х		Х	Х	Х	
TSH and T4				X ^G (Every 3 cycles)		
Urinalysis for Protein			Х ^н (Every 2 cycles)			
12-Lead ECG ^I	х			X ^J (Every 2 cycles)		
LVEF Assessment ^K				X ^L (Every 3 cycles)		
Tumor Imaging/Disease Assessment ^M			X ^N (Every 2 cycles)		x	0
Correlative Tumor Sample Collection	х	P				
AR-42 PO ^Q	Once	daily 3 days/w				
Pazopanib PO ^Q	Once daily continuously ^R					
Study Medication Diary Review & Pill Count	Х		Х	Х	х	

72

 Table 20. Study Calendar – Treatment Beginning with Cycle 2 Through Follow-Up

Table 20 Footnotes:

- A. Within 3 days prior to or on day 1 of each treatment cycle.
- B. Within 3 days prior to or on day 15.
- C. Within 2 weeks after the end of study treatment.
- D. If the patient is unable to return for a study visit at this time, the study team may contact the patient, family member, and/or other care providers to get information needed to complete the AE assessment at this time point.
- E. Include over-the-counter medications.
- F. Serum chemistry includes the following panels and tests: basic metabolic panel (sodium, potassium, carbonate, chloride, glucose, calcium, BUN, and creatinine); hepatic panel (ALT, AST, ALP, total bilirubin, direct bilirubin, albumin, and total protein); and magnesium and phosphorous. (Refer to Table 8 for instructions regarding increased frequency of liver function monitoring **[weekly for at least 4 weeks]** when pazopanib-related elevations [AST, ALT, bilirubin] occur.)
- G. Following completion of 3 cycles of study treatment beginning on day 1 of cycle 4, repeating on day 1 of cycle 7, and continuing after every 3 cycles of treatment (ie, about every 3 months).
- H. Following completion of 2 cycles of study treatment beginning on day 1 of cycle 3, repeating on day 1 of cycle 5, and continuing after every 2 cycles of treatment (ie, about every 2 months). *If urine protein is* 2+ (100 mg/dL), a 24-hour urine sample must be collected and tested.
- I. Refer to Section 6.8 and Table 7 for instructions related to QTc interval prolongation.
- J. On day 1 (+/- 1 week) of cycles 4, 6, and continuing after every 2 cycles of treatment (ie, about every 2 months [+/- 1 week]).
- K. LVEF assessment should be performed using the same method used at baseline to determine eligibility.
- L. Following completion of 3 cycles of study treatment beginning on day 1 of cycle 4 (+/- 1 week), repeating on day 1 of cycle 7 (+/- 1 week), and continuing after every 3 cycles of treatment (ie, about every 3 months [+/- 1 week]).
- M. Imaging may be limited to known sites of disease. Brain imaging required for patients with brain metastasis diagnosed and treated prior to initiation of study treatment. The imaging used at baseline should be used at each subsequent imaging time point.
- N. Following completion of 2 cycles of study treatment beginning on day 1 of cycle 3 (+/- 1 week) and continuing after every 2 cycles of treatment (ie, about every 2 months [+/- 1 week]); see Section 10.
- O. For patients who discontinued study treatment in the absence of disease progression: If it has been 8 or more weeks since the most recent disease assessment, a final on-study tumor response assessment should be performed, if possible.
- P. If not already requested during cycle 1, archived tumor samples must be requested by the end of cycle 2; see Section 11.
- Q. Refer to Section 6.2 through 6.6 for additional treatment-related instructions.

73

R. Continuing until treatment is discontinued (see Section 6.5); if the cycle has been extended to 5 weeks, AR-42 doses must be given during the 1st 4 weeks of the cycle allowing a 1-week AR-42 rest period (Section 6.2.1); pazopanib continues daily.

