6.7.4 RP2D

The RP2D may be equal to, but may not exceed, the MTD. A RP2D below the MTD may be considered given the overall tolerability of the treatment regimen including the frequency of AEs that are not DLTs and the frequency of dose modifications.

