6.8 Required QT Monitoring and QT Interval Prolongation Instructions

- 6.8.1 Monitoring
 - A 12-lead ECG and evaluation of QTc interval will be performed weekly in cycle 1, on day 1 of cycle 2, and then on day 1 of every other cycle.
 - If the QTc is ≥ grade 2, follow instructions in Table 7 for additional observation and/or ECG requirements.
 - If medically indicated, ECGs may be performed any time during treatment and follow-up.
- 6.8.2 Requirements for Manual Read of QTc Interval

Any time QTc is evaluated:

- If the HR is < 60 bpm or >100 bpm, manual read of the QT interval by a cardiologist is required; also the Fridericia formula for QT interval correction should be used (ie, QTcF).
- If HR is between 60-100 bpm, a manual read of QTc is NOT required.

Any questions or concerns about ECG readings will be reviewed with a cardiologist.

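### TSH/T4 is first repeated at cycle 4 day 1 and is not drawn at end of treatment, so patients who stop earlier have no scheduled post-baseline thyroid value (minor, cheap to improve)

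*Combined protocol and SAP*

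**What the plan says.** Table 19 marks TSH and T4 once, at screening within 14 days before cycle 1 day 1. Table 20 gives the pair a single mark, in the cycle 4 day 1 column, and footnote G sets the timing: "Following completion of 3 cycles of study treatment beginning on day 1 of cycle 4, repeating on day 1 of cycle 7", then every 3 cycles. The end-of-treatment and 30-day follow-up cells in that row are empty. Footnote A sets the day 1 window: "Within 3 days prior to or on day 1 of each treatment cycle".

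The end-of-treatment visit takes place "Within 2 weeks after the end of study treatment" (footnote C). CBC, platelets, serum chemistry and lipase are marked there. Footnote F lists the contents of the chemistry panel, and neither TSH nor T4 is among them.

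The first on-treatment scan comes earlier (footnote N): "Following completion of 2 cycles of study treatment beginning on day 1 of cycle 3 (+/- 1 week". Disease progression ends treatment (Section 6.5). Section 13.6.2 counts everyone who received any study treatment as evaluable for safety, and Section 13.4 summarises AEs by frequency and proportion.

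**The concern.** The first scan is a foreseeable exit point, and it falls one cycle before the first thyroid retest. A patient who leaves then contributes to the denominator of the safety proportions but has no scheduled test that could reveal a symptomless thyroid change. In the summary, that patient looks the same as one who was tested and found normal.

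Hypothyroidism is on the protocol's list of pazopanib warnings (Section 9.2.10). Table 17 gives it at 8% on pazopanib against 0% on placebo in soft tissue sarcoma (STS). The renal cell carcinoma (RCC) tables do not list it. At stake is how complete the descriptive thyroid safety summary is, which serves a secondary objective. At the margin it also touches Section 6.7.4, which allows an RP2D below the MTD "given the overall tolerability of the treatment regimen including the frequency of AEs that are not DLTs and the frequency of dose modifications".

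**Working it through.** The plan states no figure of its own on this point. The check is a reading of the calendar followed by a sizing under stated assumptions.

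**1. Timing.** With 4-week cycles, cycle 3 day 1 is study day 57 and cycle 4 day 1 is study day 85 (84 days elapsed). Sections 6.2.1 and 7.4 allow a cycle to be extended to 5 weeks. If all three are extended, cycle 4 day 1 is day 106 (105 days elapsed).

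**2. Can the visit windows close the gap?** The scan window is ±7 days (footnote N) and the TSH/T4 window is 3 days before to day 1 (footnote A).
- Shortest interval: (85 − 3) − (57 + 7) = 18 days.
- Longest with 4-week cycles: 85 − (57 − 7) = 35 days. A 5-week cycle 3 adds 7, giving 42 days.

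So no permitted use of the windows brings the first retest to the first scan.

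**3. Other repeated safety tests in Table 20.**

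| Test | First repeat after screening | Marked at end of treatment |
|---|---|---|
| CBC, chemistry | cycle 1 | yes |
| Lipase | cycle 2 day 1 | yes |
| ECG | cycle 1, weekly | no |
| Urine protein | cycle 3 day 1 | no |
| TSH/T4 | cycle 4 day 1 | no |
| LVEF | cycle 4 day 1 | no |

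For ECG, Section 6.8.1 says it "will be performed weekly in cycle 1, on day 1 of cycle 2, and then on day 1 of every other cycle". For urine protein, footnote H says "Following completion of 2 cycles of study treatment beginning on day 1 of cycle 3, repeating on day 1 of cycle 5". Only TSH/T4 and LVEF combine a late first repeat with an empty end-of-treatment cell.

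**4. Share off treatment before the first retest.** Inputs: median treatment duration 8.0 months in RCC (Section 1.2.1) and median PFS 4.6 months in STS (Section 1.2.2), the latter as a proxy for time on treatment. Both are for pazopanib alone. Assumption: exponential time on treatment, so p = 1 − 2^(−(days/30.44)/median). The ends of each range are all-RCC and all-STS.

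| Days elapsed | p, median 8.0 | p, median 4.6 | Of 12 at the MTD |
|---|---|---|---|
| 84 | 0.213 | 0.340 | 2.55 to 4.08 |
| 105 | 0.258 | 0.405 | 3.10 to 4.86 |

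**5. Expected missed silent hypothyroidism among 12.** The documents do not say what share is silent, so the STS rate r = 0.08 is used as if every case were. The median is 4.6 months and cycles are 4 weeks.
- Ceiling, giving early leavers the full risk: 12 × 0.08 × 0.340 = 0.33.
- Early leavers have less exposure, on average 39.1 days. With a constant hazard h = −ln(1 − r)/W, integrated over stopping times before day 84:
  - if the 8% accrues over W = 84 days, the result is 0.15;
  - if it accrues over W = 4.6 × 30.44 = 140 days, the result is 0.09.

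Table 17 gives no accrual window, so both values of W are assumptions. With all three cycles extended, the ceiling becomes 12 × 0.08 × 0.405 = 0.39, still well under one patient.

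**The case against.** The strongest reply is that nothing here is inconsistent. Table 20 follows a pattern: laboratory tests marked at each cycle's day 1 are repeated at end of treatment, and tests done at longer intervals are not. ECG and urine protein are also unmarked there. Table and footnote agree on a 3-month thyroid interval, so asking for one more draw is a preference about monitoring frequency. That stands as far as calling it an error goes. It does not remove the gap, because ECG and urine protein are both repeated before cycle 4 and TSH/T4 is not.

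Second, no decision turns on it. Table 7 starts hypothyroidism action at grade 2, and then continues pazopanib without a required reduction. A silent change found after the last dose cannot alter that patient's dosing and would hardly move an RP2D. This stands too.

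Third, events with symptoms are already captured: all AE grades are recorded to 30 days after treatment (Section 8.4), and physical examination and AE assessment take place at the end-of-treatment visit. This stands, and it limits the gap to silent changes.

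Fourth, Section 9.2.10 defers to the pazopanib prescribing information, which is not available here, and the AR-42 safety section is not in the public text. Whether a 3-month thyroid interval is clinically adequate cannot be judged from these documents, and the point does not claim that it is inadequate.

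A reader might go on to infer that LVEF should be added as well. LVEF does have the same schedule (footnote L: "Following completion of 3 cycles of study treatment beginning on day 1 of cycle 4 (+/- 1 week), repeating on day 1 of cycle 7"), but it needs a separate echocardiogram or nuclear study, so the argument of a nearly free test does not carry over. Table 7 already calls for an LVEF measurement at grade 2 heart failure.

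**Conclusion.** The gap exists, and its effect is small. About 21-34% of patients (26-41% if all three cycles run to 5 weeks) would have no scheduled post-baseline thyroid value, or about 2.6-4.1 (3.1-4.9) of the 12 at the MTD. Expected missed silent hypothyroidism with 4-week cycles is about 0.09-0.15 of 12, ceiling 0.33. These sizes rest on exponential time on treatment, on pazopanib-alone medians carried over to the combination, on PFS standing in for treatment duration in STS, and on the whole 8% being silent.

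A reader might infer that the all-treated safety denominator is wrong, or that the MTD or RP2D is compromised. The documents support neither. Counting all treated patients is sound for AEs, the DLT period is cycle 1 only, and DLT and MTD rules do not use these tests at cycle 4. The link to Section 6.7.4 is possible but thin. This is a minor, inexpensive improvement to the visit calendar.

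**What to change.** In Table 20, mark TSH and T4 in the end-of-treatment column, to be run on the blood already drawn at that visit.

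Cost: one extra assay per patient, with no new visit or procedure. Limitation: the visit may fall up to 2 weeks after the last dose, so a thyroid change may have partly recovered by then. Patients who do not attend the visit remain without a value.

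Leave the all-treated AE table, the DLT rule and the LVEF schedule as they are. Section 13.4 specifies no thyroid or LVEF table. If one is produced, showing beside it the number of patients with at least one post-baseline test would help readers tell normal from not tested, and would keep the remaining LVEF gap visible. That is optional reporting and separate from the change proposed here.

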4 PATIENT SELECTION

4.1 Inclusion Criteria

A patient must meet all of the following inclusion criteria to be eligible for this study.

- 4.1.1 Recurrent, unresectable, or metastatic RCC or STS (any histologic type) for which pazopanib is an appropriate therapy
- 4.1.2 Measurable or evaluable disease by RECIST v1.1
- 4.1.3 Age \geq 18 years
- 4.1.4 Eastern Cooperative Oncology Group (ECOG) performance status of 0 or 1 (see Appendix 1)
- 4.1.5 Adequate bone marrow function as defined below:
 - Absolute neutrophil count (ANC) ≥ 1200/mm³
 - Platelets \geq 120,000/mm³
 - Hemoglobin ≥ 9.5 g/dL

- 4.1.6 Adequate renal function as defined below:
 - Creatinine ≤ 1.5 x upper limit of normal (ULN) for the laboratory or calculated or actual creatinine clearance ≥ 60 mL/min (see Appendix 2 for the Cockcroft-Gault formula for calculating creatinine clearance)
 - Proteinuria ≤ 2+ [100 mg/dL]) using a random urine sample or < 3.0 gm using a 24-hour sample)

Note: If urine sample indicates $\ge 2+$ [100 mg/dL]), a 24-hour urine sample must be collected and tested; urine protein in the 24-hour sample must be < 3.0 gm/24 hours.

- 4.1.7 Adequate hepatic function as defined below:
 - Total bilirubin $\leq 1.5 \text{ x}$ ULN for the laboratory

Note: Patients with known Gilbert's Syndrome are **not** eligible for this study (Section 4.2.10).

- Aspartate aminotransferase (AST) ≤ 2.5 x ULN for the laboratory
- Alanine aminotransferase (ALT) $\leq 2.5 \times \text{ULN}$ for the laboratory
- 4.1.8 Non-hematologic toxicities from previous cancer therapies resolved to \leq grade 1
- 4.1.9 International normalized ratio (INR) \leq 1.5
- 4.1.10 Activated partial thromboplastin time (aPTT) \leq 1.5 x ULN for the laboratory
- 4.1.11 Left ventricular ejection fraction (LVEF) assessment (eg, echocardiogram, MUGA scan, first-pass technique) performed within 3 months prior to initiation of study treatment indicates an LVEF of ≥ 50%
- 4.1.12 A woman of childbearing potential (WCBP), defined as a woman who is < 60 years of age and has not had a hysterectomy, must have a documented negative serum pregnancy test within 7 days prior to initiating study treatment
- 4.1.13 A WCBP and a male patient with a partner who is a WCBP must agree to use a medically accepted method for preventing pregnancy for the duration of study treatment and for 2 months following completion of study treatment
- 4.1.14 Ability to understand and willingness to sign the consent form

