	 calcium abnormalities are corrected, symptoms resolved, and QTc improved to ≤ grade 1 (≤ 480ms). Reintroduce pazopanib and AR-42 with input from cardiology and with additional QTc evaluation, either concurrent with reintroduction or at earliest possible opportunity within 8 days from reintroduction. If event is thought to be related to study treatment, reduce the dose of pazopanib and AR-42 by one dose reduction step when resuming study treatment.^B Consider chronic supplementation for maintenance of electrolytes. For recurrent syncope or near-syncope thought to be related to study treatment, consider discontinuation of both pazopanib and AR-42.
Renal and Urinary Disorders	
≥ Grade 2 proteinuria	 Hold/omit^A pazopanib. If assessment of proteinuria was based on a urine dipstick reading, a 24-hour urine collection is required. Based on the 24-hour urine specimen: If grade 2 proteinuria, consult nephrology. If urine protein is < 3.0 gm/24 hours, study treatment may be continued without dose modification pending nephrology consult. If ≥ 3.0 gm/24 hours, hold study treatment until improvement to < 3.0 gm/24 hours or additional nephrology recommendations. If grade 3 proteinuria, consult nephrology and discontinue pazopanib.
Respiratory, Thoracic, and M	ediastinal Disorders
≥ Grade 2 pneumonitis	Discontinue pazopanib (also discontinue AR-42).
Skin and Subcutaneous Disc	rders
PPE (hand-foot syndrome)	See Table 9 for instructions related to PPE

Table 7. Pazopanib Dose Modification Instructions (continued)

Table 7. Pazopanib Dose Modification Instructions (continued)

Tuble III azopanie Beee mea	
Vascular Disorders	
Grade 3 hypertension defined as systolic BP >160 mmHg and diastolic BP >100 mm/Hg	 Hold/omit^A pazopanib until resolution to ≤ grade 2. Administer standard antihypertensive therapy. When resuming pazopanib, decrease pazopanib dose by one dose reduction step; monitor BP weekly for 4 weeks. If BP remains controlled for at least one cycle, the pazopanib dose may be escalated by one dose step at the investigator's discretion.
Grade 4 hypertension	Discontinue pazopanib (also discontinue AR-42)
	an the first 4 weeks of the cycle, any remaining doses for that cycle are 7.4 for additional information.

B. At the investigator's discretion (after the DLT evaluation period [Section 6.7.1]), the dose may be escalated by one dose step when the toxicity has resolved and treatment can be resumed.

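### No urine protein test is scheduled between screening and cycle 3 day 1, so a proteinuria DLT in cycle 1 would be found only by unscheduled testing

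*Combined protocol and SAP*

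**What the plan says.** **Entry.** Section 4.1.6 requires a 24-hour collection when the urine reading is 2+ or more, and then "urine protein in the 24-hour sample must be < 3.0 gm/24 hours". Any value below that limit is admissible.

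**Action on treatment.** The proteinuria row of Table 7 (Section 7.7) opens at "≥ Grade 2 proteinuria" with a pazopanib hold, and requires a 24-hour collection if the finding came from a dipstick. Within grade 2 there are two branches. One reads "If urine protein is < 3.0 gm/24 hours, study treatment may be continued without dose modification pending nephrology consult". The other reads "If ≥ 3.0 gm/24 hours, hold study treatment until improvement to < 3.0 gm/24 hours". The next step is "If grade 3 proteinuria, consult nephrology and discontinue pazopanib".

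**DLT.** Under Section 6.7.1 the DLT window is cycle 1. Under Section 6.7.2 any toxicity of grade 3 or higher attributed to either drug is a DLT unless it is on the list of exceptions. Proteinuria is not on that list.

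**Testing.** In Table 19 the row "Urinalysis for protein" carries one mark, in the screening column for the 14 days before treatment, and none on days 1, 8, 15, 22 or 29. Table 20 has no mark in cycle 2 and none at end of treatment. Its footnote H places the on-treatment tests after every two cycles, "beginning on day 1 of cycle 3, repeating on day 1 of cycle 5".

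**The concern.** The protocol has a graded action rule for proteinuria and a DLT definition that includes it, but it schedules nothing that would detect it in the period when the DLT count is made. Patients may also start close to the value at which Table 7 holds study treatment.

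The primary endpoint rests on small counts. Under Table 3, one DLT in six patients permits escalation and two mean that the MTD has been exceeded. Among the 12 patients at the MTD, three confirm it and four do not. One missed event can therefore change a decision. If an abnormal result first appears on cycle 3 day 1, nobody can say whether the event began in cycle 1, so it cannot be assigned reliably to the DLT window.

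Section 6.7.4 also lets the RP2D take account of non-DLT adverse events and dose modifications. Grade 2 proteinuria in cycles 1 and 2 would be captured only if someone happened to test for it. A patient who stops before cycle 3 may have no on-treatment urine protein result at all, yet remains in the safety population of Section 13.6.2.

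**Working it through.** This is calendar arithmetic; no power or sample-size formula applies.

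**Inputs**
- Cycle length: 28 days, extendable to 35 (Section 6.2.1).
- Screening urine sample: up to 14 days before cycle 1 day 1 (Table 19).
- First on-treatment sample: cycle 3 day 1 (Table 20 footnote H), with visits allowed up to 3 days early (footnote A).
- DLT window: cycle 1 (Section 6.7.1).
- Dosing per cycle: 28 daily pazopanib doses and 9 AR-42 doses (Sections 6.2.1 and 6.2.2).
- DLT evaluability: at least 21 pazopanib doses in cycle 1 unless a DLT has occurred (Sections 6.7.1 and 13.6.1).

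**The plan's own figure.** Section 11.3.1 equates the end of cycle 2 with about 8 weeks of treatment. 2 × 28 = 56 days, and 56 / 7 = 8.0 weeks, so the figure is reproduced.

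**Time to the first on-treatment test**

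| Case | Days after cycle 1 day 1 | Longest gap from screening sample |
|---|---|---|
| Standard cycles | 2 × 28 = 56 (8.0 weeks) | 56 + 14 = 70 days (10 weeks) |
| Standard cycles, visit 3 days early | 56 − 3 = 53 (7.6 weeks) | 53 + 14 = 67 days |
| Both cycles extended | 2 × 35 = 70 (10.0 weeks) | 70 + 14 = 84 days (12 weeks) |

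**Scheduled exposure before that test, standard cycles.** 2 × 28 = 56 pazopanib doses and 2 × 9 = 18 AR-42 doses.

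**Scheduled urine protein tests.** Cycle 1 (the DLT window): 0. Cycle 2: 0.

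**Comparison within the protocol.** In cycle 1 Table 19 schedules blood pressure, 12-lead ECG and serum chemistry (including creatinine, BUN and albumin) on days 8, 15 and 22. Hypertension and QTc prolongation, which also have rows in Table 7, are therefore looked for on a schedule. Section 6.8.1 adds that ECGs may be done at any time if medically indicated. No corresponding statement was found for urine protein.

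**What is known about frequency.** Table 14 gives all-grade proteinuria of 9% on pazopanib alone in RCC (N = 290), against 0% on placebo (N = 145). The documents give no grade 3 rate, no time to onset, no figure for the combination and no share of patients entering near 3.0 g/24 h. Proteinuria does not appear in the STS adverse-reaction tables (Tables 16 and 17). A DLT probability from these figures would be a guess, so none is given.

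**The case against.** The strongest reply is that Table 7 responds to a finding, not to a visit. AE assessments and physical examinations take place on days 8, 15 and 22 of cycle 1 and on day 1 of cycles 2 and 3, and all AEs of any grade are recorded (Section 8.4). An unscheduled urine test prompted by any of these would activate Table 7 and could establish a DLT. That stands. A reader might infer that the hold rule cannot operate for eight weeks. The documents do not support that: they forbid no unscheduled test. They do not call for one either.

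A reader might also infer that renal DLTs in general cannot be seen in cycle 1. That is wrong, because creatinine, BUN, electrolytes and albumin are measured weekly. The gap concerns proteinuria alone. Serum chemistry does not fill it, because Table 7 acts on urine protein.

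A third tempting reading is that the shared 3.0 g/24 h figure is a contradiction. It is not. Table 7 lets treatment continue below that value, which fits admitting patients below it. Nor is 3.0 g the only action point: pazopanib is first held at grade 2, and the 24-hour result decides what follows.

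It can also be said that this is only a preference about monitoring frequency, and that Section 9.2.10 refers to the prescribing information, which may advise interim testing. The prescribing information cannot be checked here. The first argument would carry weight if proteinuria were only a safety observation. Section 6.7.2 makes it part of the DLT definition, so whether it is ascertained in cycle 1 bears on the primary endpoint.

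**Conclusion.** The point holds in a limited form. Followed as written, the protocol contains no scheduled test that could trigger the Table 7 proteinuria rule before cycle 3 day 1, or show a proteinuria DLT in the DLT window. The interval is nominally 56 days from the start of treatment, and at most 70 days from the screening sample, or 84 if both cycles are extended. Only unscheduled testing could fill it.

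This rests on reading the urinalysis rows of Tables 19 and 20 as marked; footnote H confirms the cycle 3 start in words. It does not rest on any assumed event rate. The effect on the DLT count could be nil or could be one or more events, and the documents do not allow a choice between these. The change is worth making because it is cheap and because single events decide the 3+3 steps. It does not show that the escalation design or the Table 7 rules are wrong.

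**What to change.** Reconcile Tables 19 and 20 with Sections 4.1.6 and 6.7.2 and Table 7 in one of two ways:

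1. Place the existing urine protein test, with its existing 24-hour follow-up collection, at an already scheduled visit within the DLT window and before cycle 3. The sponsor chooses the visit.
2. If the gap is intended, state in Sections 6.7.2 and 13.3 that proteinuria is not systematically ascertained for DLT, and report the DLT results with that limitation.

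Neither option alters a dose, hold or discontinuation rule.

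The cost of the first option is a dipstick at a visit that already takes place, plus some extra 24-hour collections. It has one side effect to settle at the same time. A patient who entered with a reading of 2+ or more could meet Table 7's initial pazopanib hold on an unchanged baseline value, if 2+ counts as grade 2. That is an assumption, since the protocol does not define proteinuria grades. In a standard cycle 1 such a patient can lose 28 − 21 = 7 pazopanib doses before ceasing to be DLT-evaluable, or 35 − 21 = 14 if the cycle is extended. Patients who are not evaluable are replaced under Section 13.6.1. The sponsor should therefore state how a baseline reading of 2+ or more is to be handled under Table 7 when the test is repeated.
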